7 DERIVED AND COMPUTED VARIABLES

Mean change from baseline (baseline is defined in Section 12.1.4 “Definitions for Statistical Data Analysis”) is the mean of all individual subjects’ change from baseline values. Each individual change from baseline will be calculated by subtracting the individual subject’s baseline value from the value at the timepoint. The individual subject’s change from baseline values will be used to calculate the mean change from baseline.

Mean percent change from baseline is the mean of all individual subjects’ percent change from baseline values. Each percent change from baseline will be calculated by subtracting the individual subject’s baseline value from the value at the desired timepoint and then dividing this calculated value by the individual subject’s baseline value and multiplying by 100. These individual subjects’ percent changes from baseline values will be used to calculate the mean percent change from baseline.

When the baseline values is 0, 1 will be used in the denominator for calculating the percent change from baseline.

The QT interval corrected using Bazett’s formula (QTcB) will be calculated as follows:

$$QTcB = \frac{QT}{\sqrt[2]{(60/HR)}}$$

The QT interval corrected using Fridericia's formula (QTcF) will be calculated as follows:

$$QTcF = \frac{QT}{\sqrt[3]{\frac{60}{HR}}}$$

Reported BMI will be calculated at site from the body weight and height using the following formula:

$$BMI(\text{kg}/\text{m}^2) = \frac{\text{weight in kilograms}}{\text{height in meters}^2}$$

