7.3.5 Minnesota Nicotine Withdrawal Scale (revised edition) Questionnaire

The MNWS (Hughes and Hatsukami 2008) is a 24 hour recall that will be completed by the subject him/herself daily from Day 0 to Day 6, and on the second day of every visit during the ambulatory period. From Day 0 to Day 6 only, MNWS questionnaire must be asked prior to start of product use/smoking and no later than 10:00 AM. On Day 31 and Day 61 the assessment of MNWS will be conducted irrespective of the time of product use but no later than 10:00 AM. Whilst on Day 91 the assessment of MNWS has to be conducted prior to smoking but no later than 10:00 AM.

The self-reported part of the MNWS consists of the following 15 items which are rated over the last 24 hours on a scale of 0 to 4 (see Table 6). Higher scores indicate greater intensity on that scale.

The total score will be derived by calculating the average of all the non-missing data from the first 9 items. If more than 50% of the first 9 items are missing then the total score will be set to missing.

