12.6.3.1.4 Minnesota Nicotine Withdrawal Questionnaire

The MNWS will be administered daily from Days 0 to 6, and Days 31, 61 and 91 for the assessment of Day-1 to Day 5, and Days 30, 60 and 90 as it is a 24-hour recall questionnaire.

All summaries, profiles and analysis will be presented for the day before the assessment in the THS 2.2 Menthol, mCC and SA arms.

The total score, along with the percent change from baseline will be summarized. The answers to the individual questions, along with the total score, the changes and percent changes from baseline will be listed.

The profiles of the raw means from baseline to Day 90 for the total score will be plotted.

The analysis will compare each post baseline timepoint separately for the total score. An ANCOVA model will be used with terms for baseline score, sex, and average daily mCC consumption over the last 4 weeks as reported during screening. No adjustment will be made for multiple comparisons.

The SAS code to be used is similar to the model reported in Section 12.6.1.3 "Sensitivity Analysis".

LS means for each product along with the difference (THS 2.2 Menthol - mCC) and (THS 2.2 Menthol – SA) with 95% CI will be presented in the tables.

All figures, summaries and analyses will be performed on the PP Set and the FAS only.

The data will be presented in the below outputs:

TFL number	Title
FIGURES	
15.1.2.16.1	MNWS Total Score Mean and 95% CI of Percent Change from Baseline – PP Set
15.1.2.16.2	MNWS Total Score Mean and 95% CI of Percent Change from Baseline – FAS
15.1.2.17.1	MNWS Total Score Arithmetic Least Squares Means and 95% CI – PP Set
15.1.2.17.2	MNWS Total Score Arithmetic Least Squares Means and 95% CI – FAS
TABLES	
15.2.4.39.1	Descriptive Statistics of MNWS Total Score – PP Set
15.2.4.39.2	Descriptive Statistics of MNWS Total Score – FAS

TFL number	Title
15.2.4.40.1	Analysis of MNWS Total Score – PP Set
15.2.4.40.2	Analysis of MNWS Total Score – FAS
LISTINGS	
15.3.6.13	Listing of MNWS Questionnaire Results

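### Dividing by 1 when the baseline is 0 can rank MNWS percent changes in the wrong order, because most small non-zero baselines on that scale lie well below 1

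*SAP*

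**What the plan says.** SAP section 7 (Derived and Computed Variables) defines change and percent change from baseline for the whole study. On percent change it says that "Mean percent change from baseline is the mean of all individual subjects’ percent change from baseline values", and for zero baselines it adds: "When the baseline values is 0, 1 will be used in the denominator for calculating the percent change from baseline". The substituted 1 is not adapted to the unit or range of the variable.

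SAP section 7.3.5 describes the self-reported MNWS as "15 items which are rated over the last 24 hours on a scale of 0 to 4", and states that "The total score will be derived by calculating the average of all the non-missing data from the first 9 items". On direction, "Higher scores indicate greater intensity on that scale".

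SAP section 12.6.3.1.4 covers reporting: "The total score, along with the percent change from baseline will be summarized". Among the listed figures, 15.1.2.16.1 is titled "MNWS Total Score Mean and 95% CI of Percent Change from Baseline – PP Set", and 15.1.2.16.2 is the same display for the FAS. The section presents MNWS results for all three arms. The inferential part does not use percent change: "The analysis will compare each post baseline timepoint separately for the total score", by ANCOVA with baseline score as a term.

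**The concern.** A stand-in denominator does little harm if it is close to the smallest non-zero baseline the variable can take. For the MNWS total it is not. A complete total can be 0, 1/9, 2/9 and so on up to 4, so the eight values from 1/9 to 8/9 all lie below the stand-in of 1. A subject with no withdrawal symptoms at baseline is given a denominator nine times larger than a subject who scored a single point on a single item. The subject with the lower baseline can then worsen by more points and still show the smaller percent change.

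The planned summary averages these individual values by arm and plots the mean with a 95% CI. A reader using the figure to compare withdrawal across THS 2.2 Menthol, mCC and SA would see a quantity that depends partly on how many subjects in each arm sat at exactly 0 rather than just above it. That bears on the reading of an exploratory endpoint, not on any confirmatory claim.

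**Working it through.** **Inputs.** Percent change is 100 × (post − base) / base, with 1 replacing base when base = 0 (SAP section 7). The MNWS total is the mean of nine items scored 0 to 4, higher being worse (SAP section 7.3.5). With all nine items answered, the attainable totals are 0, 1/9, …, 36/9 = 4, and the smallest non-zero value is 0.111. The documents give no figure of their own on this point to reproduce.

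**The jump.**
- Baseline 0: denominator 1.
- Baseline 1/9: denominator 0.111, nine times smaller.

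**Individual values.**

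| Baseline → post | Points gained | Percent change |
|---|---|---|
| 0 → 1 | 1.000 | 1/1 = +100% |
| 1/9 → 1 | 0.889 | (8/9)/(1/9) = +800% |
| 1/9 → 6/9 | 0.556 | (5/9)/(1/9) = +500% |
| 2/9 → 7/9 | 0.556 | (5/9)/(2/9) = +250% |
| 3/9 → 1 | 0.667 | (6/9)/(3/9) = +200% |
| 0 → 4 | 4.000 | 4/1 = +400% |
| 1/9 → 5/9 | 0.444 | (4/9)/(1/9) = +400% |

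The first row worsens more in points than any of rows two to five, yet has the smallest percentage of the five. The largest worsening the scale allows (0 → 4) scores the same as a rise of 0.444 from 1/9, and half as much as the rise from 1/9 to 1.

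**When the order reverses.** Let the zero-baseline subject gain d₀ points (100 × d₀ %) and the other subject gain d points from baseline b (100 × d/b %), with d < d₀. The order reverses when d/b > d₀, that is when b × d₀ < d < d₀. This is possible only if b < 1.

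**Enumeration.** The count covers all attainable complete scores, limited to combinations in which the zero-baseline subject worsens more in points:
- other baseline 1/9 to 8/9: order reversed in 2422 of 4956 combinations (49%);
- other baseline 1 or more: 0 reversals;
- all baselines together: 2422 of 14,910 (16%).

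These are counts of possible score combinations, not expected frequencies in the trial.

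**Effect on a mean.** Take four subjects with the changes 0 → 1, 1/9 → 6/9, 2/9 → 7/9 and 3/9 → 1. The mean percent change is (100 + 500 + 250 + 200)/4 = 262.5%, and the mean absolute change is (9 + 5 + 5 + 6)/(9 × 4) = 0.694. Now let the first subject start at 1/9 instead of 0. The mean percent change becomes (800 + 500 + 250 + 200)/4 = 437.5%, while the mean absolute change falls to (8 + 5 + 5 + 6)/(9 × 4) = 0.667. The two summaries move in opposite directions. The example is illustrative only.

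**The case against.** The strongest reply is that little depends on this. MNWS is exploratory, the percent change is descriptive, and section 12.6.3.1.4 already provides results on the score scale: summaries of the total score, listed absolute changes, and ANCOVA differences (THS 2.2 Menthol against mCC and against SA) with 95% CIs. Figures 15.1.2.17.1 and 15.1.2.17.2 show least squares means. A reader might infer that percent change is the only MNWS result plotted, and that inference is wrong. This part of the reply stands and limits the point to presentation.

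A second reply is that percent change is unstable near a floor under any rule. With no zero baseline involved, 1/9 → 5/9 (+0.444) gives 400% while 2 → 4 (+2) gives 100%. That is true. It is a reason to leave percent change off this scale altogether, and it shows that editing the zero rule alone would not be enough. The zero rule still adds a separate fault, a ninefold jump in the denominator between adjacent scores.

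Third, a total of exactly 0 requires every answered item among the nine to be 0, including craving to smoke, in people who smoke at least 10 cigarettes a day. That may be uncommon. On the other hand, the baseline is taken after a day of unrestricted smoking, so low scores are plausible. The documents give no baseline MNWS distribution, so neither view can be settled from them.

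A reader might also extend the point to the Fagerström score (FTND). That does not hold. FTND is an integer sum, so its smallest non-zero baseline is already 1, and a rise of d points gives 100 × d % from a baseline of 0 or of 1. There is no jump. QSU-brief and MCEQ items run from 1 to 7 and cannot give a zero baseline.

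**Conclusion.** The point holds for the MNWS total score as a minor defect of descriptive reporting. On attainable scores, the rule can give a zero-baseline subject who worsens more a smaller percent change than a subject whose baseline lies between 1/9 and 8/9. It cannot do so against a baseline of 1 or more. The outputs exposed are the percent-change part of the MNWS summaries and Figures 15.1.2.16.1 and 15.1.2.16.2.

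It is tempting to go further and say that the plotted means are driven by this rule. The documents do not support that: without a baseline distribution, the most that can be said is that the means can be distorted. The MNWS ANCOVA, the primary biomarker analyses and the success criterion do not use these percent changes and are unaffected.

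The 1/9 steps assume complete items. With fewer items answered the step is somewhat larger (1/5 at the minimum of five allowed by the missing-item rule), so the jump shrinks to fivefold but does not disappear.

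**What to change.** In SAP section 12.6.3.1.4, summarise and plot absolute change from baseline in the MNWS total score in place of percent change. Absolute change is already defined in section 7 and already listed for this questionnaire, so no new derivation is needed. The outputs to revise are Figures 15.1.2.16.1 and 15.1.2.16.2 and Tables 15.2.4.39.1 and 15.2.4.39.2.

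In SAP section 7, replace the divide-by-1 rule with a statement that percent change is not calculated when the baseline is 0, and that the number of subjects affected is reported with each summary. Simply deleting the rule would leave a gap, because other percent changes the SAP plans could also meet a zero baseline, for example exhaled CO in ppm or Ames mutagenicity.

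The cost is a small amount of SAP wording and table and figure rework. Data collection, sample size and inferential analyses do not change.

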7.1 Biomarkers

7.1.1 Biomarkers of Exposure and Risk Markers in Urine

The adjustment of the urinary BoExp and Risk Markers concentration for creatinine will be calculated as:

$$\text{Biomarker (corrected for creatinine)} = \frac{[\text{Biomarker}]}{[\text{Creatinine}]}$$

where the [] indicates concentrations measured from the same 24 hour urine collection.

The quantity excreted for a BoExp over 24 hours will be calculated as:

$$\text{Quantity Excreted over 24 hours} = [\text{Biomarker}] * \text{urine volume}$$

where the concentration and the urine volume are from the same 24 hour urine collection.

7.1.2 Nicotine Equivalents

The quantity excreted of NEQ in 24 hours will be derived according to the formula below. The concentrations reported for free nicotine and its five major metabolites will not be used as analysis variables.

$$\begin{aligned} \text{NEQ [mg]} &= (\text{free nicotine}_c [\mu\text{mol}/\text{L}] + \text{nicotine-glucuronide}_c [\mu\text{mol}/\text{L}] \\ &\quad + \text{free cotinine}_c [\mu\text{mol}/\text{L}] + \text{cotinine-glucuronide}_c [\mu\text{mol}/\text{L}] \\ &\quad + \text{free } trans\text{-3'-hydroxycotinine}_c [\mu\text{mol}/\text{L}] \\ &\quad + \text{trans-3'-hydroxycotinine-glucuronide}_c [\mu\text{mol}/\text{L}]) \\ &\quad * 162.2[\mu\text{g}/\mu\text{mol}] * \text{urine volume (L)} / 1000 [\mu\text{g}/\text{mg}] \end{aligned}$$

N.B. All concentrations must be in $\mu\text{mol}/\text{L}$ before applying the above formula.

The conversion factors will be applied as follows:

Free nicotine	The molecular weight is 162.232 g/mol (Chemical Information Specialized Information Services RN:54-11-5). Therefore to convert nicotine from ng/mL to nmol/L, the result in ng/mL is multiplied by 6.164.
Nicotine glucuronide	The molecular weight is 338.356 g/mol (Chemical Information Specialized Information Services RN:152306-59-7). Therefore to convert nicotine from ng/mL to nmol/L, the result in ng/mL is multiplied by 2.955.
Cotinine	The molecular weight is 176.218g/mol (Chemical Information Specialized Information Services RN:486-56-6). Therefore to transform cotinine from ng/mL to nmol/L, the result in ng/mL will be multiplied by 5.675.
Cotinine-glucuronide	The molecular weight is 352.341 g/mol (Chemical Information Specialized Information Services RN:139427-57-9). Therefore to transform cotinine from ng/mL to nmol/L, the result in ng/mL will be multiplied by 2.838.
Trans-3'hydroxycotinine	The molecular weight is 192.217 g/mol (Chemical Information Specialized Information Services RN:34834-67-8). Therefore to transform trans-3' hydroxycotinine from ng/mL to nmol/L, the result in ng/mL is multiplied by 5.202.
Trans-3'hydroxycotinine-glucuronide	The molecular weight is 368.34g/mol (Chemical Information Specialized Information Services RN:132929-88-5). Therefore to transform trans-3' hydroxycotinine from ng/mL to nmol/L, the result in ng/mL is multiplied by 2.715.

The adjustment of NEQ for creatinine in urine will be calculated as:

$$\text{NEQ (corrected for creatinine)} = \frac{[\text{NEQ}]}{[\text{Creatinine}]}$$

where the concentrations are measured from the same 24 hour urine collection.

7.1.3 CYP1A2

CYP1A2 activity is calculated as the molar metabolic ratio of PX / CAF in plasma, both expressed in molar equivalent (nmol/L).

The conversion factor will be applied as follows:

PX	The molecular weight is 180.166 g/mol (Chemical Information Specialized Information Services RN:611-59-6). Therefore to convert PX in ng/mL to nmol/L the result in ng/mL is multiplied by 5.550.
----	---

CAF

The molecular weight is 194.193 g/mol. (Chemical Information Specialized Information Services RN:58-08-2). Therefore to convert CAF in ng/mL to nmol/L the result in ng/mL is multiplied by 5.150.

The converted results will be calculated to three decimal places and the ratio will be reported as a percentage with two decimal places.

If either of the PX or CAF concentration is LLOQ then the ratio will not be calculated.

7.1.4 CYP2A6

CYP2A6 activity is calculated in plasma as the metabolic ratio of trans-3' hydroxycotinine to cotinine, both expressed in molar equivalent (nmol/L) (Jacob et al. 2011).

The conversion factor will be applied as follows:

Cotinine

The molecular weight is 176.215 g/mol (Chemical Information Specialized Information Services RN:486-56-6). Therefore to transform cotinine from ng/mL to nmol/L, the result in ng/mL will be multiplied by 5.675.

Trans-3'hydroxycotinine

The molecular weight is 192.217 g/mol (Chemical Information Specialized Information Services RN:34834-67-8). Therefore to transform trans-3' hydroxycotinine from ng/mL to nmol/L, the result in ng/mL is multiplied by 5.202.

The converted results will be calculated to three decimal places and the ratio will be reported as a percentage with two decimal places.

If either of the cotinine or trans-3'hydroxycotinine concentration is LLOQ then the ratio will not be calculated.

7.2 Pharmacokinetic Parameters

The peak nicotine and cotinine plasma concentration (C_{peak}) and time to peak concentration (t_{peak}) will be obtained directly from the concentrations taken on Day 5. If the peak concentration occurs at more than one time point then t_{peak} will be assigned to the first value. The weighted average concentration over 24 hours on Day 5 (C_{avg}) will be calculated by dividing the area under the curve from 0 to 24 h ($AUC_{0-24\ h}$) by 24, where the $AUC_{0-24\ h}$ is calculated using the linear trapezoidal rule.

Since the samples are taken whilst the subjects are smoking freely all samples must be non-missing for the parameters to be calculated as C_{peak} (and t_{peak}) could occur at any time.

7.3 Questionnaires

7.3.1 Socio-Economic Status Questionnaire

On Day 4, subjects will fill a socio-economic status (SES) questionnaire. Subjects will be asked a series of questions related to their education, occupation, size and monthly income of their household.

7.3.2 Fagerström Test for Nicotine Dependence (FTND)

The FTND will be used in its revised version (Heatherton et al 1991), as updated in 2012 (Fagerström et al. 2012). These questions are to be answered by the subject themselves. It is conducted at Screening to determine subject's dependence on nicotine and on the Day 90 Visit to assess any changes in their dependence on nicotine.

Table 3 describes the six questions the questionnaire consists of, and the scores associated with each question.

The FTND total score will be derived by summing the individual item scores if all items are non-missing, otherwise the total score will be set to missing. For the FTND total score, descriptive statistics and frequency tables according to the following classification will be provided (Fagerström et al. 2012):

Mild	0 – 3
Moderate	4 – 6
Severe	7 – 10

**Table 3: Scoring for the Fagerstrom Test for Nicotine Dependence**

	FTND Question	Response	Score
1	How soon after you wake up do you smoke your first cigarette?	Within 5 minutes	3
		6 to 30 minutes	2
		31 to 60 minutes	1
		After 60 minutes	0
2	Do you find it difficult to refrain from smoking in places where it is forbidden?	Yes	1
		No	0
3	Which cigarette would you hate most to give up?	The first one in the morning	1
		Any other	0
4	How many cigarettes per day do you typically smoke?	10 or less (up to ½ pack)	0
		11 to 20 (a little more than ½ pack, up to a full pack)	1
		21 to 30 (a little more than a pack, up to 1½ packs)	2
		31 or more (more than 1½ packs)	3
5	Do you smoke more frequently during the first hours after waking than during the rest of the day?	Yes	1
		No	0
6	Do you smoke if you are so ill that you are in bed most of the day?	Yes	1
		No	0

7.3.3 Questionnaire of Smoking Urges-Brief (QSU-brief)

The QSU-brief (Cox et al. 2001) is a self-reported questionnaire completed on a daily basis from Day -1 to Day 5, and on every visit during the ambulatory period, i.e., Day 30 Visit (Day 30), Day 60 Visit (Day 60), and Day 90 Visit (Day 90).

The QSU-brief consists of 10 items as presented in Table 4.

**Table 4: Questionnaire of Smoking Urges Brief - Questions and Factors**

	Question	Factor
1	I have a desire for a cigarette right now	1
2	Nothing would be better than smoking a cigarette right now	2
3	If it were possible, I probably would smoke now	1
4	I could control things better right now if I could smoke	2
5	All I want right now is a cigarette	2
6	I have an urge for a cigarette	1
7	A cigarette would taste good now	1
8	I would do almost anything for a cigarette now	2
9	Smoking would make me less depressed	2
10	I am going to smoke as soon as possible	1

All items will be rated on a 7-point scale, ranging from 1 (strongly disagree) to 7 (strongly agree). Higher scores indicate a higher urge to smoke.

Two factor scores and a total score will also be derived (Cox et al. 2001). Each factor is a subset that includes 5 of the 10 questions as defined in Table 4. Factor 1 represents the desire and intention to smoke with smoking perceived as rewarding, while Factor 2 represents an anticipation of relief from negative effect with an urgent desire to smoke.

The factors and total scores will be calculated by averaging non-missing item scores if at least 50% are non-missing, otherwise the factor or total score will be set to missing.

7.3.4 Modified Cigarette Evaluation Questionnaire

The MCEQ (Cappelleri et al. 2007) will be completed by the subject him/herself on a daily basis from Day -1 to Day 5 and on every ambulatory visits on Day 30 Visit (Day 30), Day 60 Visit (Day 60), and Day 90 Visit (Day 90). On Day -1 and Day 0, all subjects will complete the questionnaire. From Day 1 onwards, only subjects who are randomized to the THS 2.2 Menthol and mCC arms will complete this questionnaire.

The MCEQ consists of 12 items as presented in Table 5.

**Table 5: Modified Cigarette Evaluation Questionnaire - Questions and Subscales**

	Question	Subscale
1	Was smoking satisfying?	Smoking Satisfaction
2	Did cigarettes taste good?	Smoking Satisfaction
3	Did you enjoy the sensation in your throat and chest?	Enjoyment of Respiratory Tract Sensations
4	Did smoking calm you down?	Psychological Reward
5	Did smoking make you feel more awake?	Psychological Reward
6	Did smoking make you feel less irritable?	Psychological Reward
7	Did smoking help you concentrate?	Psychological Reward
8	Did smoking reduce your hunger for food?	Psychological Reward
9	Did smoking make you dizzy?	Aversion
10	Did smoking make you nauseous?	Aversion
11	Did smoking immediately relieve your craving for a cigarette?	Craving Reduction
12	Did you enjoy smoking?	Smoking Satisfaction

Items are assessed on a 7-point scale, ranging from 1 (not at all) to 7 (extremely). Higher scores indicate greater intensity on that scale.

The subscales scores will be derived by averaging the individual non-missing item scores if at least 50% are non-missing, otherwise the subscale score will be set to missing.

